Secondary Endpoints 1:	
Mean differences (within treatments over time and between treatments at specified time points) in:
 
 Time-to-Maximum Glucose Infusion Rate (GIR) ($t_{max(GIR)}$) Time to half-maximal GIR, both early and late ($t_{50(GIR),early}$ & $t_{50(GIR),late}$) Onset of action as measured by a drop of blood glucose (BG) by 5 mg/dL Duration of insulin action (calculated the same as MRT for PK) GIR_{max} Area under the GIR curve ($AUC_{0-t(GIR)}$), both absolute and as a percentage of total $AUC_{0-\infty}$ and Coefficient of Variation (CV) of $AUC_{0-t(GIR)}$, where $t = 5, 10, 15, 20, 30, 45, 60, 90, 120, 150, 180, 210, 240,$ and 300 min 
Other PD parameters may also be calculated.

Secondary Objective 2:	To assess pharmacokinetic (PK) parameters within and across treatments following subcutaneous delivery using Achilles vs Teflon control set on DOI and days 3, 5, and 7 post insertion.
Secondary Endpoints 2:	
Mean differences (within treatments over time and between treatments at specified time points) in:
 
 • Early exposure ($AUC_{0-60min}$) • Mean-residence time (MRT) of insulin • Maximum Insulin concentration (C_{max}) • Time-to-Maximum Insulin Concentration (t_{max}) • Time-to-50% Maximum Insulin Concentration [$t_{50,early}$ & $t_{50,late}$], both early (i.e. before C_{max}) and late (i.e. after C_{max}) • $AUC_{(0-t)}$ (both absolute and as a percentage of $AUC_{(0-300)}$) and Coefficient of Variability (CV) $AUC_{(0-t)}$ where $t = 3, 6, 9, 12, 15, 20, 25, 30, 35, 40, 45, 50, 60, 70, 80, 90, 105, 120, 150, 180, 210, 240$ and 300 min 
Other PK parameters may also be calculated.

Secondary Objective 3:	To assess continuous glucose monitoring (CGM) data, comparing data within and across treatments.
Secondary Endpoints 3:	
 • Mean daily time in range (70-180 mg/dL), DOI through Day 7 inclusive • Mean daily time in target (70-140 mg/dL), DOI through Day 7 inclusive • Mean and median daily glucose, DOI through Day 7 inclusive • Glucose variability (%CV), DOI through Day 7 inclusive • Mean daily time ≤ 70 mg/dL, < 54 mg/dL, DOI through Day 7 inclusive • Mean daily time > 140 mg/dL, > 180 mg/dL, > 240 mg/dL, DOI through Day 7 inclusive • Other CGM metrics may also be calculated
Secondary Objective 4:	To assess performance of investigational infusion set on DOI through 7 for each treatment

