Alsted studied extended wear of up to 7 days, assessing PK on DOI and days 1, 2, 4 and 7. Overall PK exposure (AUC_{0-4hr}) was steady over 4 days, with progressive acceleration of t_{max} over that interval ($p < .02$). By day 7 t_{max} was still accelerated as compared to DOI but, AUC_{0-4hr} was reduced by approximately 21% ($p < .04$). The author hypothesized that these changes were due to alterations in local adipose tissue blood flow (ATBF) although attempts to measure this directly were inconsistent, with an apparent increase in ATBF initially, reverting to baseline by day 4. Efforts to document increased local cytokine levels were hampered by technical issues. (*Alsted TS. Device-induced subcutaneous trauma. PhD Thesis. Department of Histology & Delivery, Novo Nordisk A/S, Denmark & Department of Biomedical Sciences, Faculty of Health Sciences, University of Copenhagen, Denmark, November 2010*).

Summarizing these various studies of cannula wear time, it appears that insulin exposure is accelerated during the first few days of CSII cannula wear, and this results in improved response to glucose challenge. With further wear time, PK exposure diminishes. These findings provide challenges for persons with diabetes, who may have to adjust insulin doses and meal strategies as insulin exposure first accelerates and then wanes over cannula wear time.

Effect of dispersed insulin delivery on PK:

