9.4 STATISTICAL ANALYSES

9.4.1 GENERAL APPROACH

As a routine evaluation of the data during analysis, consistency of the study variables to properties of statistical tests will be checked. The parameter for the primary analysis will be log-transformed, and the rest of the PK as well as PD parameters will be log-transformed as appropriate before analysis. With categorical data, exact statistical test procedures will be used to minimize test assumptions, except when Wilson Score confidence intervals can be calculated.

All data will be tested for normality using the Shapiro-Wilk test. Data that is highly skewed or contains outliers even after the log transformation will be analyzed using the rank transformation, namely analyzing the ranks of the assessments within the combined sample. The paired measurements will be analyzed with dependent *t* tests or Wilcoxon signed rank tests, as indicated. AUC data will be calculated with the trapezoidal rule for defined PK/PD time points. Post hoc analyses will be performed after confirmation of significant main effects. Unless otherwise specified, data will be reported as mean \pm SD with $p < 0.05$ considered statistically significant.

A data convention used in this analysis is as follows: for tabulated continuous variables, the descriptive analyses will present the mean, standard deviation, median, minimum and maximum. And for tabulated categorical variables, the number with the characteristic, the total number evaluated, the percent and the 95% Wilson Score confidence intervals will be provided.

For secondary endpoint analyses, two-tailed significance tests will be performed with significance level $p = 0.05$.

For the estimation of catheter failures, we used data from the study of Patel *et al.* who investigated steel and Teflon infusion sets worn over a 7-day period.⁵ They reported that 42% of participants could consistently wear an infusion set for 6-7 days (58% failure) without a deterioration in glucose levels. It should be noted that their failure rate also included accidental removal of catheters, removal due to pain, and removal due to poor adhesion of catheter pad (total 32%). Since our participants will be in a more controlled setting (i.e. clinical research staff will be inserting and carefully securing the devices

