9.4.3 ANALYSIS OF THE SECONDARY ENDPOINT(S)

Secondary analyses will use the both ITT and PP populations for analysis.

The survival of the Achilles and control infusion sets will be compared using a discrete lifetable analysis over study days 0, 3, 5, and 7 and the discrete form of the log-rank test.

All pharmacokinetic parameters (AUCs , t_{50} , C_{max} , t_{max} , MRT for the insulin concentration by time curve, etc.) will be estimated using non-compartmental models and log-transformed before analysis. Means for the two treatment groups will be compared in a mixed-effects (repeated-measures) linear model with treatment and period as fixed effects and participant as a random effect. The mean difference between treatments (on the log-scale) will be compared with a two-sided test using significance level $\alpha=0.05$. Then mean ratio and its 95% confidence interval will be calculated by inverse-transforming the mean difference and its 95% confidence interval.

All pharmacodynamic parameters (AUCs , onset time and time to return to baseline for the glucose concentration by time curve, etc.) will be estimated using non-compartmental models. Means for the two treatment groups will be compared in a mixed-effects (repeated-measures) linear model with treatment and period as fixed effects and participant as a random effect. The mean difference between treatments will be compared with a two-sided test using significance level $\alpha=0.05$. Wilcoxon signed rank tests will be used if the data is significantly skewed.

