4.4.4.2.2 PK Parameters

All pharmacokinetic parameters will be presented descriptively.

Additionally, AUCs, t_{50} , C_{max} , t_{max} , and MRT will be tested for treatment effects. The effects between Achilles and control set will be compared in a mixed-effects (repeated-measures) linear model with *treatment* and *period* as fixed effects and *participant* as a random effect. Log-transformation will be applied if data distribution is found to be highly skewed.

The mean difference between treatments (or on the log-scale) will be compared with a two-sided test using significance level $\alpha=0.05$. Then mean ratio and its 95% confidence interval will be calculated

- Inverse-transforming will be done if the variable was log-transformed.

Population	ITT and PP (ITT is the primary , PP is the sensitivity)
------------	---

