4.4.4.2.3 PD Parameters

All PD parameters will be presented descriptively.

Additionally, AUCs, t_{50} , GIR_{max} , $t_{max(GIR)}$, and Duration of Insulin Action will be tested for treatment effects. The effects between Achilles and control set will be compared in a mixed-effects (repeated-measures) linear model with *treatment* and *period* as fixed effects and *participant* as a random effect. Log-transformation will be applied if data distribution is found to be highly skewed.

The mean difference between treatments (or on the log-scale) will be compared with a two-sided test using significance level $\alpha=0.05$. Then mean ratio and its 95% confidence interval will be calculated

- Inverse-transforming will be done if the variable was log-transformed.

Secondary analyses will use the both ITT and PP populations for analysis. Multiple comparisons may raise these tests. We are not considering any correction in this SAP.

Population	ITT and PP (ITT is the primary , PP is the sensitivity)
------------	---

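### The secondary PK and PD tests pool all clamp days into one treatment difference, so they do not test the stated by-day and over-wear endpoints

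*SAP*

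**What the plan says.** **Endpoints.** Protocol 1.1 (Secondary Endpoints 1 and 2) sets the PD and PK endpoints as "Mean differences (within treatments over time and between treatments at specified time points) in" listed parameters. The matching objectives (Protocol 3.2, SAP 2.2) name DOI and days 3, 5 and 7.

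**PD tests.** SAP 4.4.4.2.3 compares the sets in a "linear model with *treatment* and *period* as fixed effects and *participant* as a random effect". It then says: "The mean difference between treatments (or on the log-scale) will be compared with a two-sided test".

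**PK tests.** SAP 4.4.4.2.2 uses the same model: "AUCs, t_{50} , C_{max} , t_{max} , and MRT will be tested for treatment effects".

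**Protocol version.** Protocol 9.4.3 says: "Means for the two treatment groups will be compared in a mixed-effects (repeated-measures) linear model with treatment and period as fixed effects". It names no day term either.

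**Related provisions.**
- SAP 4.4.4.1 contrasts the slopes of GIR AUC0-300 over days 0, 3, 5 and 7, and repeats this for the baseline-adjusted AUC0-300.
- Protocol 9.4.9 adds day as a main effect for PK and plans within-treatment trend tests, as exploratory work.
- Protocol 9.4.1 states: "Post hoc analyses will be performed after confirmation of significant main effects".

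**The concern.** The endpoint has two parts: the difference between sets at each clamp day, and the change within each set over wear. The planned model estimates neither. It returns one average difference per parameter over whichever clamps were done.

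The study asks whether the sets diverge as wear goes on, so timing matters. The protocol's own literature summary describes exposure that first accelerates and later wanes. In the cited seven-day wear study, "Overall PK exposure (AUC_{0-4hr}) was steady over 4 days", with a fall of about 21% by day 7. If the sets differ in that way, an average over four days dilutes the late difference, and an early difference in the other direction offsets it. A significant pooled result would not show when the difference arose.

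The gap affects Cmax, tmax, t50, MRT and the insulin AUCs, and on the PD side GIRmax, tmax(GIR), t50(GIR) and duration of action. The primary slope contrast covers none of these.

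**Working it through.** **1. Endpoint against test**

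| Stated endpoint component | Term needed | In SAP 4.4.4.2.2, 4.4.4.2.3 and Protocol 9.4.3? |
|---|---|---|
| Achilles minus control at DOI, days 3, 5, 7 | treatment-by-day | No |
| Change over wear within each set | day within treatment | No |
| Difference averaged over clamps | treatment | Yes |

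This part needs no arithmetic.

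**2. Inputs** (Protocol 9.2, SAP 3.4): total variance of ln GIR AUC0-300 is 0.21, of which 40% is within participant (0.084). The within-participant correlation is autoregressive with r = 0.5. The lag unit is not stated, so both readings (per visit / per day) are shown. The slope difference is 0.07, taken as per day. The late loss is 21% (Protocol 2.2.3), so −ln(0.79) = 0.236. Assumption: the ln GIR AUC variances hold for the other parameters, for which the documents give none.

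For contrast weights w over days 0, 3, 5, 7 and correlation matrix R:

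SE = √(2 × 0.084 × w′Rw / n); power is two-sided at 0.05, from the noncentral t on n − 2 df.

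**3. The plan's own figure.** It states 90% power at 24 participants for the primary slope. With w = (−3.75, −0.75, 1.25, 3.25)/26.75, w′Rw = 0.0364 / 0.0395 and SE = 0.0160 / 0.0166. Power is 98.7% / 98.0%, and 90% needs 16 / 17 participants. The stated inputs do not reproduce 90% at 24. A within share of 60% with per-day lags would give 90.8%, but the text says 40%. No power is stated for the PK/PD tests, so only the variances carry over.

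**4. Dilution in the pooled mean** (weights ¼ each)
- Linear, 0.07 per day: (0 + 0.21 + 0.35 + 0.49)/4 = 0.2625, which is 54% of the day-7 difference of 0.49.
- Day 7 only: 0.236/4 = 0.059, or 25%.
- Illustrative reversal (0, −0.20, 0, +0.236): 0.036/4 = 0.009.
- A constant offset of 0.059 on every day gives the same pooled mean as a 0.236 loss at day 7 only. The pooled test cannot tell them apart.

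**5. Power at n=24, complete data.** Pooled: w′Rw = 0.516 / 0.341, SE = 0.060 / 0.049. Day 7: SE = √(2 × 0.084/24) = 0.084.

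| Pattern of difference | Pooled | Day-7 contrast | Slope |
|---|---|---|---|
| 0.07 per day, linear | 99% / >99% | >99% | 99% / 98% |
| 0.49 at day 7 only | 50% / 67% | >99% | 94% / 93% |
| 21% reached linearly by day 7 | 52% / 70% | 77% | 52% / 49% |
| 21% at day 7 only | 16% / 21% | 77% | 40% / 38% |

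**6. At n=7**, the number who had completed when the study was stopped (SAP 2.5): for a 21% loss at day 7 only, about 7-8% pooled and 24% for day 7.

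**7. Missing late clamps.** Protocol 9.4.1 assumes 40-50% set failures, and a removed failed set gets no clamp (Protocol 1.3, footnote 6). Assume clamps available at 100/90/75/55% on days 0/3/5/7. The pooled mean then keeps about 15-16% of a day-7-only difference and 44% under the linear pattern (simulation). With 50-60% available at day 7, power of the day-7 contrast for a 21% loss falls to roughly 50-60% (generalised least squares, normal approximation).

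**The case against.** **A late loss is mostly missed.** A reader might infer this, but the documents do not support it in general. Under the steady 0.07-per-day divergence on which the trial was sized, the pooled test has about 99% power. A 21% loss reached linearly gives 52-70%. Serious loss of power needs a difference concentrated at day 7, and complete data make the gap look its largest, because missing late clamps also weaken the day-7 contrast.

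**The plan gives no inference on change over wear.** This is also too strong. The primary analysis contrasts slopes of GIR AUC0-300. Whether that contrast can be estimated from the model as written is a separate question. Protocol 9.4.9 plans within-treatment PK trends, and SAP 2.5 does not list their removal among its changes. These routes are partial: the first covers one GIR variable, and the second is exploratory, limited to PK and without treatment-by-day.

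**Other routes.** Protocol 9.4.1 mentions paired tests without tying them to any day or endpoint. Its main-effects condition need not mean treatment only. Neither provision specifies a by-day comparison.

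**By-day tables.** The default layout in SAP 4.4.2 is by treatment and period, but it yields to specific descriptions. Protocol 9.4.8 plans listings by time point, and the table list is a separate file. Absence of by-day tables cannot be inferred. Descriptive tables would still not be tests.

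**Inputs.** The 21% refers to insulin exposure and the variance to GIR AUC, so the power figures are indicative.

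**Early termination.** This stands as a limit on practical effect: with seven completers no test of a 21% loss is informative.

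**Conclusion.** The mismatch holds on the text alone. Followed exactly, the secondary PK/PD analyses never test the differences at each clamp day or the change over wear that the protocol names as endpoints. The numerical consequence depends on the pattern. A difference confined to day 7 is cut to a quarter, with power of about 16-21% pooled against 77% for day 7 when the loss is 21% at n=24. A steady divergence at the design value is detected but not located in time. These figures assume complete clamps, ln GIR AUC variances for all parameters, r = 0.5 on either lag reading and a 0.07 slope per day. The point should be fixed because the change is cheap. It does not show that the trial would fail to see every loss of insulin effect.

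**What to change.** In SAP 4.4.4.2.2 and 4.4.4.2.3, and in Protocol 9.4.3:
- Add categorical day and treatment-by-day to the PK/PD models, and state the within-period covariance. With participant as the only source of correlation and r = 0.5 per visit within periods, simulation of the pooled test (participant entered as fixed) gave a false-positive rate of about 20%.
- Report Achilles minus control with 95% CI at DOI and days 3, 5 and 7, and each set's change from DOI with 95% CI, as the analysis of the stated endpoints.
- Keep the pooled difference as a summary.
- State that the by-day estimates do not depend on a significant treatment main effect, and amend the sentence in Protocol 9.4.1 to match.

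Cost: SAP wording and extra table rows, with no new data. Day-specific intervals are wider than the pooled one (SE 0.084 against 0.049-0.060 at n=24), and there are more comparisons, for which SAP 4.4.4.2.3 plans no correction. With seven completers a model this size may not fit for every parameter, so the by-day results should be presented as estimates with intervals.

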9.4.9 EXPLORATORY ANALYSES

Exploratory analyses will use the both ITT and PP populations for analysis. All pharmacokinetic parameters (AUCs, t_{50} , C_{max} , t_{max} , MRT for the insulin concentration by time curve, etc.) will be estimated using non-compartmental models and log-transformed before analysis. Means for the two treatment groups will be compared in a mixed-effects (repeated-measures) linear model with treatment, day and period as fixed effects and participant as a random effect. The mean difference between treatments (on the log-scale) will be compared with a two-sided test using significance level 0.05. Then mean ratio and its 95% confidence interval will be calculated by inverse-transforming the mean difference and its 95% confidence interval. Trends over time within treatments will be compared with two-sided tests using significance level $\alpha=0.05$.

Kaplan-Meier device survival curves will be constructed for each device and then compared with a Cox regression analysis with a frailty term that accounts for the repeated-measures on participants.

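### At least 12 secondary PK and PD device comparisons are each tested at two-sided 0.05 with no correction or hierarchy, so the secondary family-wise error is uncontrolled while the protocol calls any p<0.05 statistically significant

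*SAP*

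**What the plan says.** - **SAP 4.4.4.2.2 (PK).** The parameters compared between devices are MRT, tmax, Cmax, t50 and the AUCs. Of these the section says that they "will be tested for treatment effects. The effects between Achilles and control set will be compared in a mixed-effects (repeated-measures) linear model". The level is two-sided 0.05 for each.
- **SAP 4.4.4.2.3 (PD).** The parameters are GIRmax, tmax(GIR), t50, the AUCs and the duration of action. The list ends with the words "and Duration of Insulin Action will be tested for treatment effects"; here too each test is at two-sided 0.05. The section closes its discussion of testing with "Multiple comparisons may raise these tests. We are not considering any correction in this SAP".
- **Protocol 9.4.1.** The rule reads "For secondary endpoint analyses, two-tailed significance tests will be performed with significance level"; the figure given there is 0.05. The same section makes p<0.05 the general criterion for statistical significance.
- **Protocol 1.1, Secondary Endpoints 1 and 2.** The endpoints are "Mean differences (within treatments over time and between treatments at specified time points) in" the listed parameters. AUC(0-t) is listed at 23 cut-points for PK and 14 for PD.
- **Protocol 9.4.9.** The PK parameters appear again, now under exploratory analyses and with a different model: "Means for the two treatment groups will be compared in a mixed-effects (repeated-measures) linear model with treatment, day and period as fixed effects". Protocol 9.4.3 and SAP 4.4.4.2.2 treat the PK comparison as secondary, with treatment and period only.

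No key secondary endpoint is named, and no secondary test depends on the primary result. The SAP has no exploratory section.

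**The concern.** The SAP sees that many tests will be run and declines to adjust for them, but does not say how the results may be read. The protocol does supply a reading, which is that each p-value below 0.05 is statistically significant. Together these let any one of a dozen or more contrasts be reported as a device difference, with no statement of how often that would happen by chance.

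The early stop makes this more pressing. SAP 2.5 says the study was terminated after the 7th participant completed, against 24 in the sample-size justification. An inconclusive primary contrast is therefore plausible, and attention may then move to the secondary results.

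**Working it through.** The plan states no number of tests and no family-wise error rate, so there is no figure of its own to reproduce. The only stated input is the per-test level of 0.05, two-sided.

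**1. Count of tests.**

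SAP 4.3.2.4.2 and 4.3.2.5.8 define t50 as two variables (early and late) for both PD and PK.

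- Smallest reading, one AUC per family: 1 AUC + 2 t50 + 1 maximum + 1 tmax + 1 MRT or duration = 6. For PK and PD together, 6 + 6 = 12.
- Widest reading, all synopsis cut-points: PK 23 + 2 + 1 + 1 + 1 = 28; PD 14 + 2 + 1 + 1 + 1 = 19; total 47.

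Neither count includes the log-rank test on set survival or the per-protocol repeats, which are labelled sensitivity analyses.

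**2. Independent tests.**

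P(at least one false positive) = 1 − 0.95^k.

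- k = 12: 1 − 0.95^12 = 0.460
- k = 47: 1 − 0.95^47 = 0.910

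**3. Correlated tests.**

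The documents give no correlation between endpoints, so a range is assumed. Equicorrelated normal test statistics were simulated (200,000 per case), taking P(any |Z| > 1.96):

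| Assumed correlation | 12 tests | 47 tests |
|---|---|---|
| 0.5 | 0.320 | 0.608 |
| 0.8 | 0.186 | 0.293 |
| 0.9 | 0.134 | 0.190 |
| 0.95 | 0.105 | 0.136 |

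**4. Small-sample version.**

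With 2x2 crossover t tests and 7 participants (5 df), 12 tests give 0.354 at correlation 0.5 and 0.160 at 0.9. With 24 participants, 12 tests give 0.329 at 0.5. Sample size hardly matters.

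**5. Curve-based version.**

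Equal correlation is a poor description of the 47 tests, because 37 of them (23 + 14) are nested cumulative areas from the same two curves. One-peak PK and PD profiles were therefore simulated under no device difference, with assumed variances, and every parameter was derived from them.

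| Participants | 12 tests | 47 tests |
|---|---|---|
| 7 | 0.240 | 0.263 |
| 24 | 0.235 | 0.255 |

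The average per-test error in these runs was 0.054 and 0.048, so the excess comes from multiplicity and not from a faulty individual test. Going from 12 to 47 tests adds only about 2 percentage points.

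**The case against.** The best defence is that this is a Phase 1b study with one stated statistical hypothesis, and unadjusted secondary tests are common at that stage. The SAP is open about making no correction. It also narrows testing: SAP 4.4.4.2.4 makes the other efficacy endpoints descriptive, and SAP 4.4.5.6 makes VAS descriptive although Protocol 9.4.4 planned a test. Neither document announces a device claim from a secondary p-value.

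Much of this stands, and it limits the point. It does not remove it. Disclosure says that no correction is made, but not that the p-values are nominal, and Protocol 9.4.1 says the opposite.

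Some stronger readings are tempting and should not be adopted:

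- **A false significant result is more likely than not.** For 12 tests the chance is below one half even under independence. It passes one half only for 47 tests at low to moderate correlation, which nested AUCs do not support.
- **The SAP literally plans 47 tests.** It says only AUCs. The cut-points are in the protocol synopsis, and the planned tables are in an attached file that is not part of the text available here. SAP 2.5 adds that some outputs may not be produced.
- **Within-treatment and by-day comparisons add to the SAP's tests.** The synopsis lists them as endpoints, but SAP 4.4.4.2.2 and 4.4.4.2.3 test treatment effects only.
- **The PK contrast will be reported with two p-values.** The SAP does not carry the Protocol 9.4.9 model forward. What stands is that the documents give two statuses and two models, and do not say which governs.

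The 7-participant figures use completers, while the ITT population needs only one completed clamp. The results at 24 are close, so this does not change the conclusion.

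**Conclusion.** The point holds as a matter of uncontrolled error in the secondary family. For 12 tests the family-wise error is about 0.13 to 0.32 at assumed correlations of 0.9 to 0.5, or 2.7 to 6.4 times the nominal 0.05, and 0.46 if the tests are independent. The curve-based check gives about 0.25 for either count, roughly five times nominal. These figures rest on assumed correlations or variances, because the documents give none, and on each test holding its own 5% level.

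A reader might infer that the primary result is compromised. It is not: the slope contrast is a separate test and its error is unchanged. A reader might also infer that Protocol 9.4.1 protects the family by allowing post hoc analyses only after a significant main effect. That works within one endpoint and not across endpoints.

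This is a worthwhile and cheap correction to what the trial may conclude from its secondary results.

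**What to change.** Replace the sentence in SAP 4.4.4.2.3 that declines correction, and apply the new text to SAP 4.4.4.2.1 to 4.4.4.2.3:

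> The only confirmatory test is the ln(AUC0-300(GIR)) slope contrast in the ITT population. All secondary PK, PD and set-survival comparisons are reported as estimates with 95% confidence intervals. Any p-value is nominal and unadjusted. No secondary result is described as statistically significant or used to claim a difference between devices. For secondary endpoints this overrides the significance convention in Protocol 9.4.1.

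Two reconciliations are needed with it:

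1. SAP 4.4.4.1 opens by naming infusion-set failure rate as the primary endpoint. Protocol 1.1, 9.1 and 9.2 and SAP 3.4 rest on the slope. The SAP must state one primary endpoint, or the new text will contradict it.
2. State which single PK model is used: treatment and period (Protocol 9.4.3, SAP 4.4.4.2.2), or with day added (Protocol 9.4.9). The two should not be declared the same analysis, because they are not.

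Recording the override in SAP 2.5, which already lists departures from the protocol's statistical section, keeps the change within the SAP. Amending the protocol itself would need IRB approval. The cost is SAP wording and table footnotes, with no new data and no division of alpha. The sponsor gives up significance language for secondary results. Because the change only restricts claims, adopting it late cannot favour the investigational set.
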